6.12.6.1 Hematology

Hematological data will be recorded at Screening, Baseline, Surgery, Hospital Discharge and Follow-up (after 30, 60, 120 and 180 days from Surgery): Red Blood Cells (RBC), Hematocrit, Hemoglobin, White Blood Cells (WBC), Mean Cellular Hemoglobin (MCH), Mean Cellular Hemoglobin Concentration (MCHC), Mean Cellular Volume (MCV), Erythrocyte Sedimentation Rate (ESR), Fibrinogen, Platelet Count.

Summary statistics as denoted under 2.-4. will be presented.

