7.3.2. Stopping Rules

If one of the following occurs during the enrollment period of patients receiving the test article (sFilm-FS) the study will be immediately suspended:

- Three or more patients developed a suspected unexpected serious adverse reaction (SUSAR) caused by a TBS post-operative re-bleeding (not requiring surgery re-intervention);
- Two or more patients had a TBS re-bleeding events following final observation period that required surgery re-intervention;
- Three or more patients developed other possible serious adverse reactions like thromboembolic events or severe allergic reactions.
- Three or more patients develop serious unanticipated or unexpected local reactions (serious adverse events) such as:
 - Signs of local reactions affecting the spleen and liver (persistent pain in the area of the application that is unanticipated or unexpected)
 - Persistent unanticipated and unexpected Systemic inflammatory response syndrome (SIRS), defined with at least two of these conditions: body temperature over 38 or under 36 degrees Celsius, heart rate greater than 90 beats/minute or respiratory rate greater than 20 breaths/minute or partial pressure of CO₂ less than

- 32 mmHg, leucocyte count greater than 12000 or less than 4000 /microliters or over 10% immature forms or bands
- Reactions on other local organs such as adhesions and reactions impacting the intestinal tract etc., assessed as being due to local reactivity. This would be diagnosed as a bowel obstruction that is unanticipated.

These stopping rules only apply to the investigational treatment group (Group A). The active-comparator group (Group B) patients should be followed according to the Investigator's standard practice as clinically appropriate.

After study suspension, the Data Safety Monitoring Board (DSMB), together with the Sponsor, will review the data and decide whether to continue or terminate the study.

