11.1.4. Visit 4 [Day 1 to Day of Hospital Discharge (D-HD)]

On Day 1 after surgery and until the day of hospital discharge, daily assessment will be conducted and will include:

- Vital signs (blood pressure, heart rate, temperature, respiratory rate).
- Blood hematology and biochemistry (see Schedule of Assessments for the list of tests).
- Adverse events (in particular related to post-operative adhesions, systemic inflammation, bleeding / thrombotic and transfusion-related complications).
- Transfusion requirements.
- Concomitant medications.

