⁴ Urine analysis tests include: specific gravity, pH, glucose, protein, blood, ketones, microscopic examination.

⁵ A serum sample will be collected and stored at -70°C for possible future viral safety testing.

⁶ Measurement of levels of antibodies against Human Fibrinogen and Human Thrombin. For this purpose, a serum sample will be collected and stored at -70°C for testing at the end of the study.

⁷ Additional MRI will be performed throughout the study if the investigator identifies signs and symptoms of unanticipated or unexpected persistent inflammatory response, or unexplained abdominal pain or other symptoms (for instance signs of adhesions, bowel obstruction, etc.).

⁸ Operative/surgical information include OR time, procedure time, time from liver resection/incision to initiation of fascial closure, drain usage, estimated blood loss, cell salvage use, transfusion information (if applicable), length of stay (ICU and overall LOS).

⁹ Intra-operative details include hepatic parenchyma classification type (normal or abnormal, steatotic, cirrhotic or other), Investigator description of the TBS (area, density, arterial/venous/mixed, intensity of flow), alternative methods used to achieve hemostasis (if applicable), estimated TBS treated area and total resected area, number of product units applied at the TBS and at other areas rather than the TBS, incidence of post-operative bile leaks requiring intervention, hepatic segment information (anatomic resection/non-anatomic resection).

¹⁰ Patients will be monitored for absence of bleeding at 2, 3, 5, 7, and 10 minutes after product application and thereafter, before closing the site.

¹¹ Assessments to be taken daily from one day after surgery (D1) until hospital discharge (D-HD).

	STATISTICAL ANALYSIS PLAN	FSTAT.01.03
Study Code: HEM-HEM-01-17		Sealantium Medical Ltd.

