6.12 Safety Evaluation

As previously stated, Safety is the primary endpoint.

Safety could be a composite endpoint because include more than one variable:

- ✓ Adverse Events
- ✓ Thrombotic Events
- ✓ Transfusion-Related Complications
- ✓ MRI Assessment (post-operative adhesions)
- ✓ Signs of Systemic Inflammations
- ✓ Antibodies against Fibrinogen and Thrombin
- ✓ Physical Examination
- ✓ Vital Signs
- ✓ Blood and Coagulation Parameters
- ✓ Urine Analyses

All Safety data will be listed by patients and treatment groups at each collected time and tabulated with the appropriate descriptive statistics by treatment groups at each collected

	STATISTICAL ANALYSIS PLAN	FSTAT.01.03
Study Code: HEM-HEM-01-17		Sealantium Medical Ltd.

time.

Considering that no hypothesis testing for difference between treatments groups concerning AEs related to bleeding at TBS and the other safety data was planned in the protocol, only 95% confidence limits on differences between treatments will be done.

Concerning safety data, an independent data review will be done by a medical reviewer before data review meeting and database lock. The medical reviewer will identify and classify all safety endpoints with respect to e.g. thrombotic events, transfusion complications, etc. and will check correctness of MeDDRA classification (PT, SOC). At the end of this review, medical reviewer will be produced a detailed report.

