6.12.5 Vital Signs and Physical Examination

6.12.5.1 Vital Signs

Vital signs, including systolic (mmHg), diastolic blood pressure (mm Hg), heart rate (beats/min), respiratory rate (breath/min) and body temperature (°C), are measured at Screening, Baseline, Surgery, Post- Surgery, Hospital Discharge and Follow-up (after 30, 60, 120 and 180 days from Surgery). Summary statistics for each of these parameters will be presented by treatment group at each time point.

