6.12.6.2 Biochemistry

Biochemistry data will be recorded at Screening, Baseline, Surgery, Hospital Discharge and Follow-up ((after 30, 60, 120 and 180 days from Surgery): Blood Urea Nitrogen (BUN), Creatinine, Glucose, Lactate Dehydrogenase (LDH), Total Proteins, Albumin, Total Bilirubin, Uric acid, Aspartate Transaminase (AST), Alanine Amino Transferase (ALT), Gamma Glutamyl Transferase (GGT), D-Dimer, C-Reactive Protein (CRP), Anti-thrombin and Lactate, Sodium, Calcium, Phosphorus.

Summary statistics as denoted under 2.-4. will be presented.

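### The SAP hematology and biochemistry sections leave the daily post-operative samples off their time points, and systemic inflammation, a named part of the primary endpoint, has no patient-level analysis of its own

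*SAP*

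**What the plan says.** Protocol 11.1.4 (Visit 4) states: "On Day 1 after surgery and until the day of hospital discharge, daily assessment will be conducted and will include" vital signs, hematology and biochemistry, and adverse events, with systemic inflammation among the events singled out. The flow chart in SAP 3.1 repeats this: its footnote 11 marks Visit 4 vital signs and Visit 4 hematology and biochemistry as daily.

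The SAP analysis sections differ from each other. On hematology, 6.12.6.1 reads "Hematological data will be recorded at Screening, Baseline, Surgery, Hospital Discharge and Follow-up", followed by the four follow-up days. On biochemistry, 6.12.6.2 reads "Biochemistry data will be recorded at Screening, Baseline, Surgery, Hospital Discharge and Follow-up", with the same four days. On vital signs, which share the daily schedule, 6.12.5.1 says they "are measured at Screening, Baseline, Surgery, Post- Surgery, Hospital Discharge and Follow-up".

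SAP 3.3.1 and protocol 12.1 make signs of systemic inflammation part of the primary endpoint, and SAP 6.12 lists "Signs of Systemic Inflammations" among its safety variables. Protocol 13.1 leaves the assessment to the investigator, using temperature, heart rate, respiratory rate, white cell count and CRP, without thresholds. Protocol 7.3.2 contains a systemic inflammatory response definition, "defined with at least two of these conditions", as part of a stopping rule.

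**The concern.** The days between surgery and discharge are when changes in hemoglobin, white cells, CRP and D-dimer are most likely, and the protocol samples daily for that reason or one like it. Two of the sections that tell the programmer what to summarise jump from surgery to discharge. One of them holds the white cell count and the other holds CRP, the two laboratory measures on which protocol 13.1 bases the inflammation assessment.

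The second gap compounds the first. By-visit summaries of each measure taken separately cannot show how many patients had two abnormal signs at the same time. A named component of the primary endpoint could then reach the report without a statement of how many patients in each arm had it.

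**Working it through.** The plan gives no figure on this point. The check is a comparison of texts plus one small count.

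**Step 1. Time points for hematology and biochemistry**

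| Visit | Flow chart (protocol 2, SAP 3.1) | SAP 6.12.6.1 and 6.12.6.2 | SAP 6.12.5.1 (vital signs) |
|---|---|---|---|
| Screening | yes | yes | yes |
| Baseline | yes | yes | yes |
| Surgery | yes | yes | yes |
| Visit 4, daily | yes | **no** | yes |
| Discharge | yes | yes | yes |
| Days 30, 60, 120, 180 | yes (4) | yes (4) | yes (4) |
| Total | 9 | 8 | 9 |

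Visit 4 is the only difference. The coagulation and urine sections (6.12.6.3 and 6.12.6.4) match the schedule, which has no daily samples for those tests.

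**Step 2. Samples outside the named time points**

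Inputs: 15 patients per arm (protocol 14.1). Discharge day D is not given; D = 5 to 10 is assumed. Visit 4 runs from Day 1 to the day before discharge (protocol 7.1), and the discharge sample belongs to Visit 5, which the SAP names.

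- Per patient: D − 1, so 5 − 1 = 4 to 10 − 1 = 9.
- Per arm: 15 × 4 = 60 to 15 × 9 = 135.
- Share of a patient's scheduled draws, (D − 1) / (8 + D − 1), if Visit 2 is not skipped: 4/12 = 33% to 9/17 = 53%.

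In the SAP lists, the only sample named between the day of surgery and Day 30 is the one at discharge.

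**Step 3. Where each component in SAP 6.12 is analysed**

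- Adverse events: 6.12.2
- Thrombotic events: 6.12.3
- Transfusion-related complications: 6.12.1
- MRI, adhesions: 6.12.4
- Antibodies: 6.12.6.7
- Physical examination: 6.12.5.2
- Vital signs: 6.12.5.1
- Blood and coagulation: 6.12.6.1 to 6.12.6.3
- Urine: 6.12.6.4
- Systemic inflammation: none

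Nine of ten components have a section.

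**Step 4. Whether the adverse event tables fill the gap**

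Under protocol 13.1 an abnormal laboratory result is an adverse event only if it comes with significant clinical signs or symptoms or needs therapy. A patient can therefore show inflammatory signs without entering the adverse event tables. Those tables (SAP 6.12.2) run by system organ class and preferred term, with no grouping for inflammation.

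**The case against.** The best defence is that the daily data are covered elsewhere. SAP 6.12 promises that all safety data will be listed and tabulated at each collected time. SAP 6.12.6 promises listings at each time point, summaries by time point and shift tables for any post-baseline value. Protocol 14.8.6 lists every laboratory value recorded. The sentences in 6.12.6.1 and 6.12.6.2 speak of recording, not of summarising, and the mock tables are a separate document not available here. On inflammation, the investigator assesses it, adverse events related to it are sought at every post-operative visit, and a medical reviewer is to classify all safety endpoints.

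Much of this stands. A reader might infer that the daily samples are excluded from analysis, or that inflammation is never counted. The documents do not support either reading: the general rules reach the daily data, the five component measures are each summarised, and inflammation reported as an adverse event is counted in the tables of 6.12.2.

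The defence does not remove the conflict. The lists act as time-point specifications everywhere else: vital signs, coagulation and urine match the schedule. The specific sections also narrow the general one in another respect. Item 5 of 6.12.6 gives change from baseline to all continuous parameters, but the two sections call only for items 2 to 4. The general text therefore does not settle what is programmed. Even under it, no rule says how to summarise repeated daily values over stays of different length. The medical reviewer's task does not name inflammation and gives no criteria. The MRI section mentions an inflammatory response only as a trigger for imaging.

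A further objection is that worst-value tables are a matter of taste in a descriptive study with 15 patients per arm. No planned inference changes, and that is a fair limit on the weight of the point.

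**Conclusion.** The point holds as an inconsistency and a gap, not as lost data. Two SAP sections name eight time points where the schedule has nine, and one primary-endpoint component of ten has no analysis section, hence no specified patient count by arm beyond reported adverse events. It should be corrected because it concerns the primary endpoint and a better method is available from data already collected. Sample size and error rates are unaffected.

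The figure of 60 to 135 samples per arm rests on an assumed discharge on Day 5 to 10. Multiplying 15 by 5 to 10 days would give 75 to 150, but with those discharge days it counts the discharge sample, which the SAP does name.

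A reader might also take the two-condition definition in protocol 7.3.2 as the definition of the endpoint component. The documents do not say so. That definition serves a stopping rule for Group A only, limited to persistent, unexpected and serious cases. For the safety assessment, protocol 13.1 relies on investigator judgement and includes CRP, which 7.3.2 does not. The two passages must be reconciled by the sponsor.

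**What to change.** 1. In SAP 6.12.6.1 and 6.12.6.2, add Post-Surgery (daily, Day 1 to discharge) to the time points.
2. In the same sections, tabulate by arm each patient's worst post-operative white cell count, CRP, D-dimer and hemoglobin, stating the direction for each. This gives one value per patient whatever the length of stay. A longer stay gives more chances of an extreme value, so show the number of days sampled alongside.
3. Add a short subsection to SAP 6.12 giving, by arm:
   - (a) the number of patients with systemic inflammation as assessed by the investigator under protocol 13.1;
   - (b) a descriptive count of patients with at least two abnormal signs together, on any day and on consecutive days, from the temperature, heart rate, respiratory rate and white cell count already collected.
4. Label (b) as a partial version of the definition in protocol 7.3.2, because partial pressure of CO₂ and immature forms are not on the scheduled test list.
5. Have the sponsor reconcile protocol 7.3.2 and 13.1 on how inflammation is defined, and state the outcome in the SAP.

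The cost is SAP wording and a few more tables, with no new data. SAP section 2 places finalisation after the blind data review and before database lock, so the change belongs there.

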6.12.6.2 Biochemistry

Biochemistry data will be recorded at Screening, Baseline, Surgery, Hospital Discharge and Follow-up ((after 30, 60, 120 and 180 days from Surgery): Blood Urea Nitrogen (BUN), Creatinine, Glucose, Lactate Dehydrogenase (LDH), Total Proteins, Albumin, Total Bilirubin, Uric acid, Aspartate Transaminase (AST), Alanine Amino Transferase (ALT), Gamma Glutamyl Transferase (GGT), D-Dimer, C-Reactive Protein (CRP), Anti-thrombin and Lactate, Sodium, Calcium, Phosphorus.

Summary statistics as denoted under 2.-4. will be presented.

6.12.6.3 Coagulation

Coagulation data will be recorded at Screening, Baseline, Surgery, Hospital Discharge and Follow-up ((after 30 and 180 days from Surgery): Prothrombin Time (PT), Partial Prothrombin Time (PTT) and International Normalized Ratio (INR).

Summary statistics as denoted under 2.-4. will be presented.

6.12.6.4 Urine

Urine analysis data will be recorded at Screening, Baseline, Surgery, Hospital Discharge and Follow-up ((after 30 and 180 days from Surgery): pH, Specific Gravity, Glucose, Protein, Blood and Ketones.

Summary statistics as denoted under 1.-4. will be presented.

	STATISTICAL ANALYSIS PLAN	FSTAT.01.03
Study Code: HEM-HEM-01-17	Sealantium Medical Ltd.	

6.12.6.5 Pregnancy Test

Pregnancy test data will be listed.

6.12.6.6 Thrombelastography (TEG) Reaction Time

Date of TEG, reaction time (min) and maximum amplitude (mm) of TEG, will be summarized with descriptive statistics for patients having data available. Note that TEG was removed in protocol 5.0 of 08JUL2021.

6.12.6.7 Immunogenicity - Antibodies against Human Fibrinogen and Thrombin

Values below lower limit of quantitation will be left missing for analysis. As antibody tests can undergo a second testing in case of positive tests the reconfirmed value will be taken for analysis in case of discrepancies.

Number and percentage of patients having positive/ negative results at each visit and over all visits will be tabulated.

Data on Human Antibodies against Fibrinogen and Thrombin levels will be summarized by time point with descriptive statistics for positive results.

	STATISTICAL ANALYSIS PLAN	FSTAT.01.03
Study Code: HEM-HEM-01-17		Sealantium Medical Ltd.

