6 STATISTICAL ANALYSIS METHOD

6.1 General Principles

In general, categorical data will be presented using counts and percentages, whilst

	STATISTICAL ANALYSIS PLAN	FSTAT.01.03
Study Code: HEM-HEM-01-17		Sealantium Medical Ltd.

continuous variables will be presented using the mean, standard deviation, standard error of mean, median, minimum, maximum and number of patients. Minima and maxima will usually be reported to the same level of accuracy as the raw data; means, medians, will be presented to one further decimal place; standard deviations and standard errors will be presented to 2 decimal places more than the raw data. Percentages will be rounded to the nearest integer or with one decimal. In tabulations, denominators for calculation of percentages will be taken as the number of non-missing responses in the specified analysis population and treatment group unless otherwise stated. 95% Clopper-Pearson Confidence Intervals for the means or the percentages will be produced if appropriate to explain the results [1].

Table will display data for each treatment group and overall (=Total column).

All data recorded in the CRF will be listed and sorted by treatment groups, subject number and visits [See Appendix 1].

Considering that the study is designed as phase I/II, in which phase I concerns to the primary endpoint (Safety) and phase II concerns to the preliminary data on effectiveness of sFilm-FS, data will not be presented in the two distinct frames, phase I and phase II.

The probability level for all analyses will be set at 5% and appropriate 95% Confidence Intervals will be produced according to the nature of the variables and will be based on a valid case approach, if so [e.g. percentages will be based on the number of observations available at the specific time point and not based on the number of patients at the visit.

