6.5 Handling of Missing Values

In accordance with the Study Protocol, no substitution or specific approach for missing data will be applied.

	STATISTICAL ANALYSIS PLAN	FSTAT.01.03
Study Code: HEM-HEM-01-17		Sealantium Medical Ltd.

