6.12.6 Clinical Laboratory Data

Results for each parameter at each time point and treatment will be presented as listing, low (L) and high (H) values will be flagged in listings; in the listing will be reported the normal range of each parameter processed, too. The following table will be used for all laboratory parameters:

	STATISTICAL ANALYSIS PLAN	FSTAT.01.03
Study Code: HEM-HEM-01-17		Sealantium Medical Ltd.

1. Summary statistics in terms of number and percentages for categorized parameters will be generated by time point and treatment.
2. In case of continuous measurements descriptive statistics will be presented by time point.
3. Normal, abnormal Not Clinically Significant (NCS) and abnormal Clinically Significant (CS) counts and frequency classifications will be tabulated for all parameters having recorded data about.
4. Shift tables will show changes in frequency of normal, abnormal NCS and abnormal CS values for any post-baseline value compared to Baseline.
5. All continuous parameters will show tables with absolute change from Baseline.

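### Setting antibody results below the quantitation limit to missing can, with the SAP's default denominator, remove negative patients and overstate the antibody-positive rate

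*SAP*

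**What the plan says.** SAP 6.12.6.7 opens with the rule "Values below lower limit of quantitation will be left missing for analysis". It does not limit that rule to any particular table. For positive tests that are repeated, "the reconfirmed value will be taken for analysis in case of discrepancies". The section then asks for two outputs:

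- A classification table: "Number and percentage of patients having positive/ negative results at each visit and over all visits will be tabulated". No denominator is given.
- A summary of antibody concentrations, in which "levels will be summarized by time point with descriptive statistics for positive results".

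The default denominator is in SAP 6.1: "denominators for calculation of percentages will be taken as the number of non-missing responses" in the analysis population and treatment group, unless otherwise stated. The same section adds a valid-case rule: each percentage rests on the results on hand at a time point, whatever the number of patients seen. SAP 6.5 says that "no substitution or specific approach for missing data will be applied".

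Antibodies to both proteins are a named part of the primary safety endpoint (Protocol 12.1, SAP 3.3.1), and both proteins are components of the product (Protocol 5.1). The schedule of assessments describes the test as a measurement of antibody levels. Neither document gives the quantitation limit (LLOQ), the positivity cut-point, or whether the laboratory returns its own positive/negative call.

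**The concern.** A result below LLOQ is an observed low result. For a positive/negative classification it is the clearest kind of negative. If it is stored as missing and the table divides by non-missing responses, the patient leaves the denominator while every quantifiable positive stays in both numerator and denominator. The error then runs one way: the positive percentage can only rise or stay the same.

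At stake is one component of the primary safety endpoint, in a trial with about 15 patients per arm, where losing a few patients from a denominator moves a percentage a long way. SAP 6.12 also plans confidence limits on treatment differences for safety data. If the number of results below LLOQ differs between arms, the arms would be compared on differently selected subsets.

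**Working it through.** **1. Check of the interval method.** The only precision figure in the documents is in Protocol 14.8.2: 80% of 15 patients, exact 95% CI 52% to 96%. The Clopper-Pearson limits for x out of n are

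- lower = 2.5% quantile of Beta(x, n − x + 1)
- upper = 97.5% quantile of Beta(x + 1, n − x)

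With x = 12 and n = 15 these give 51.9% to 95.7%, which reproduces the stated figure. This validates the method only; it is not an immunogenicity figure.

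**2. Inputs.** Patients per arm: 15 (Protocol 14.1, SAP 3.4). The number of positives x and the number of results below LLOQ b are not in the documents. I assume x from 0 to 3, and b of 5, 10 or all non-positives.

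**3. The two readings.**

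- Negatives kept: rate = x / 15
- Results below LLOQ dropped as missing: rate = x / (15 − b)

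**4. Results (rate, exact 95% CI in %).**

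| Positives x | Negatives kept, x/15 | b = 5, x/10 | b = 10, x/5 | All non-positives below LLOQ |
|---|---|---|---|---|
| 0 | 0% (0 to 21.8) | 0% (0 to 30.8) | 0% (0 to 52.2) | 0/0, undefined |
| 1 | 6.7% (0.2 to 31.9) | 10% (0.3 to 44.5) | 20% (0.5 to 71.6) | 1/1 = 100% (2.5 to 100) |
| 2 | 13.3% (1.7 to 40.5) | 20% (2.5 to 55.6) | 40% (5.3 to 85.3) | 2/2 = 100% (15.8 to 100) |
| 3 | 20.0% (4.3 to 48.1) | 30% (6.7 to 65.2) | 60% (14.7 to 94.7) | 3/3 = 100% (29.2 to 100) |

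For x = 0 the upper limit is 1 − 0.025^(1/n): 21.8% at n = 15, 30.8% at n = 10 and 52.2% at n = 5.

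**5. Does the missing rule reach the classification table?** The wording does not exclude it. The level summary is already restricted to positive results, so there the rule could matter only for a sample called positive with a level below LLOQ. A rule with almost no work to do in the level summary is naturally read as applying to the other output as well. Nothing in SAP 6.12.6.7 overrides the default denominator. Where the SAP wants a different one it says so, as in SAP 6.12.1 for transfusion percentages.

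**The case against.** The strongest reply is that the same section orders negatives to be tabulated, so its authors cannot have meant them to vanish. On that reading the missing rule concerns the numeric value, and positive/negative is a separate classification. Protocol 11.2 fits this: a central laboratory does the testing, and a positive result triggers a confirmatory sample. The default denominator also yields to other instructions, and the mock tables, held in a separate document, may settle the matter. This stands as far as it goes. If the laboratory reports its own call and the table uses it, nothing is inflated. But neither document says that such a call exists, and the rule as written does not depend on one.

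A second reply is that the harm is limited: the trial is descriptive, has no hypothesis tests, and lists safety data by patient, so an odd denominator would be visible. That lowers the stakes but does not make the printed percentage right.

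Two stronger readings are tempting, and the documents do not support them:

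- A reader might infer that mean antibody levels are shifted upward. The level summary is confined to positives by design and labelled that way. If results below LLOQ are negative, leaving them missing does not alter that table.
- A reader might infer that patients who become positive lose their change from baseline, because SAP 6.12.6 states "All continuous parameters will show tables with absolute change from Baseline". It is not clear that this covers antibodies. The haematology, biochemistry and coagulation subsections call up items 2 to 4 of that list and urine items 1 to 4. The immunogenicity subsection calls up none and names its own two outputs. The by-visit table shows a switch from negative to positive without any numeric change.

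**Conclusion.** The point holds as a conditional one. The written rules, followed literally, allow negative patients to be dropped and the antibody-positive rate to be overstated. They do not establish that it will be overstated.

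Under the assumed 15 per arm and 2 positives, the printed rate lies between 13.3% (negatives kept) and 100% (all 13 others below LLOQ and dropped), with 20% and 40% at 5 and 10 dropped. The 100% figure is the extreme and should not be quoted alone: if the cut-point lies above LLOQ, negatives between the two stay in the denominator. With no positives the percentage is not overstated; only the upper limit rises, or the rate becomes undefined.

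The size therefore depends on three facts the documents do not give: whether a separate call exists, where LLOQ lies relative to the cut-point, and how many results fall below LLOQ. The flaw goes beyond missing detail, because a stated rule can produce a wrong number for a named component of the primary endpoint. It should be corrected before database lock.

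**What to change.** Replace the opening sentence of SAP 6.12.6.7 with a rule that says:

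1. A result below LLOQ is classified as negative, including when it is the confirmatory result used in place of an earlier one.
2. The denominator of the positive/negative table is all patients with an evaluable sample at that visit, or at any visit for the overall row.
3. The missing rule applies only to the numeric level summaries, and the number of results below LLOQ is shown beside them.

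If the laboratory does supply its own positive/negative call, say so in the same place; the denominator still needs stating.

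The cost is one short rule in the SAP and a check that the mock table matches. No new data are needed. Substituting a fixed value for results below LLOQ is not needed, and it would sit badly with the SAP 6.5 position against substitution.
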